3 STUDY POPULATIONS

Infants, between the age of 1 to 12 months, with one of following congenital heart diagnoses, in need of total corrective and elective heart surgery: 1) Non-restrictive VSD, Tetralogy of Fallot, acyanotic AVSD.

3.1 Definition of Study Populations

3.1.1 *Intent-to-Treat Population (Full Analysis Set)*

All randomized subjects with at least one creatinine measurement at follow-up (24h, 48h, 72h or 96h) will be included in the Intent-to-Treat (ITT) population.

3.1.2 *Per-Protocol Population*

All ITT subjects with no major protocol violations which can affect the creatinine values will be included in the Per Protocol (PP) population. The final decisions regarding the PP population will be taken at the Clean File meeting before the database lock.

3.1.3 *Safety Population*

All enrolled subjects who received study drug will be included in the safety population.

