### 7.1.7 Definitions of serious adverse event (SAE)

A serious adverse event is an AE occurring during any study phase (i.e, run-in, treatment, wash-out, follow-up), that fulfils one or more of the following criteria:

- Results in death
- Is immediately life-threatening
- Requires in-patient hospitalisation or prolongation of existing hospitalisation
- Results in persistent or significant disability or incapacity
- Is a congenital abnormality or birth defect
- Is an important medical event that may jeopardise the subject or may require medical intervention to prevent one of the outcomes listed above.

For reporting purposes, any suspected transmission via a medicinal product of an infectious agent is also considered an SAE and is reported in an expedited manner. Any organism, virus or infectious particle (for example prion protein transmitting Transmissible Spongiform Encephalopathy), pathogenic or non-pathogenic, is considered an infectious agent.

For further guidance on the definition of a SAE, see Appendix B to the Clinical Study Protocol.

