### **7.1.13 Randomization code breaking**

If an AE is assessed to be a SAE or SUSAR, the study code will be broken, the infusion of the study medicine will be terminated and prompt measures for reversing the course of the events will be taken until stability is reached. The patient will be followed up as long as medically indicated. The patient will be included in the intention-to-treat-analysis and described in the Clinical Study Report

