4.4 Efficacy Variables/Endpoints

4.4.1 Primary endpoint

AKI_(48 hours) is defined as 50% increase in corrected creatinine within 48 hours. AKI_(48 hours) is calculated using screening creatinine (uncorrected) compared to 24 and 48 hours corrected creatinine.

Corrected creatinine [(creatinine (μmol/ml)/1000 x [1 + (fluid balance (L)_(+24 hours) / (weight (kg x 0.6)))] only calculated for day 1-3. For example for day 1 the Fluid balance measured at day 2 will be used. If negative values in fluid balances, fluid balance is set to 0.

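### The SAP's intention-to-treat set requires a follow-up creatinine, which conflicts with protocol 7.1.13, and the 48-hour AKI endpoint has no rule for death or a missing 48 h value

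*SAP*

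**What the plan says.** **Population.** SAP 3.1.1 admits to the intention-to-treat population "All randomized subjects with at least one creatinine measurement at follow-up (24h, 48h, 72h or 96h". The safety population, by contrast, needs only receipt of study drug.

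**Protocol commitment.** Section 7.1.13 opens "If an AE is assessed to be a SAE or SUSAR, the study code will be broken", ends the infusion, and then says: "The patient will be included in the intention-to-treat-analysis and described in the Clinical Study Report". Section 7.1.7 lists "Results in death" first among the SAE criteria, so every early death falls under this rule.

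**Endpoint.** SAP 4.4.1 makes the primary outcome binary: AKI "is defined as 50% increase in corrected creatinine within 48 hours". On the derivation it says: "AKI_(48 hours) is calculated using screening creatinine (uncorrected) compared to 24 and 48 hours corrected creatinine". On the fluid correction it says: "For example for day 1 the Fluid balance measured at day 2 will be used". Neither 4.4.1 nor the primary analysis in 5.5.1 (logistic regression on treatment group) mentions death, withdrawal or a single missing value.

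**Deviations and changes.** SAP 5.3 calls it a major deviation if the day-1 and day-2 creatinine are both missing, and a minor one if either is missing. SAP section 7, meant for changes from the protocol, holds only an instruction to list them.

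**The concern.** Membership of the primary analysis set depends on something observed after randomisation. Whether an infant has a follow-up creatinine can depend on how the infant fared, and so on the treatment. The protocol also breaks the code on an SAE and lets the investigator withdraw infants for safety concerns or complications (4.4), so some decisions that determine whether a later sample exists may be taken with the arm known. An intention-to-treat analysis is meant to exclude this route to bias.

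The endpoint gap adds to the problem. Two programmers could code the same infant differently without departing from the SAP. Protocol 1.3 describes creatinine as a late marker of AKI, so a lone 24 h value leans towards no event. With 35 infants per arm, each one is 1/35 = 2.9 percentage points of the arm's event rate.

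**Working it through.** **1. Tracing infants through the two documents**

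| Infant | In SAP 3.1.1 set? | 48-hour AKI under SAP 4.4.1 | Protocol 7.1.13 |
|---|---|---|---|
| Dies, or has an SAE and leaves, before any follow-up creatinine | No | None | Must be included: direct conflict |
| Leaves without an SAE before any follow-up creatinine | No | None | Not covered; departs from the intention-to-treat principle only |
| Has a 24 h sample, dies before the day-2 fluid balance | Yes | Not computable by the literal formula; no AKI if the correction is taken as zero and the value is normal | Included, but no scoring rule in either document |
| Has a normal 24 h value with its fluid balance, no 48 h value | Yes | Open: missing, or no AKI from one value | Included if an SAE occurred; no scoring rule |
| Has only 72 h or 96 h values | Yes | None | Serves the 72 h and 96 h analyses in SAP 5.5.2 |

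The conflict is exact in the first row. The third and fourth rows are the endpoint gap. The fifth means that the 48-hour AKI denominator in Table 14.3.1, titled as ITT, need not equal the size of that set.

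**2. The plan's own figure**

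The only planning figure is 35 per arm, for a 20% creatinine reduction at 80% power. No SD is given, so it cannot be reproduced. Solving backwards at two-sided 0.05, CV = 0.20 / [(1.960 + 0.842) × √(2/35)] = 0.299. This point does not rest on that figure and uses only the arm size. No allowance for losses is stated.

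**3. Size, with assumed counts**

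The documents give no design AKI rate and no rate of early death or withdrawal, so all counts here are assumptions.

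Take 8/35 AKI on levosimendan and 16/35 on milrinone, with an unadjusted logistic (Wald) test:

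- OR = (8/27) / (16/19) = 0.35
- SE of log OR = √(1/8 + 1/27 + 1/16 + 1/19) = 0.526
- z = 1.98, p = 0.047

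Now let k of the 27 levosimendan infants without recorded AKI be early deaths:

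| k | Excluded | Scored AKI-free | Counted as event |
|---|---|---|---|
| 1 | 8/34, p = 0.056 | 8/35, p = 0.047 | 9/35, p = 0.084 |
| 2 | 8/33, p = 0.068 | 8/35, p = 0.047 | 10/35, p = 0.141 |

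The crossing depends on the starting table. From 6/35 v 14/35 (p = 0.039), excluding one such infant leaves p = 0.045, while counting that infant as an event gives 0.072.

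Losses in the other arm can work against levosimendan. With 7/35 v 15/35 the likelihood-ratio p is 0.038. If two of the 15 milrinone events were early deaths counted as events and are instead removed, 7/35 v 13/33 gives p = 0.078.

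The loss of power from exclusion is minor. For assumed rates of 50% v 25%, power is 0.582 at 35 per arm and 0.557 at 33. The issue is bias and an undefined outcome.

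**The case against.** **Most infants with an SAE are not lost.** Ending the infusion does not end measurement. Creatinine is taken daily by routine (protocol section 3) and every morning in PICU (7.1.5), and SAEs are followed up after discontinuation (4.4). An infant who survives an SAE will normally have a sample and stay in the set. This stands, and it narrows the conflict to infants with no sample at all.

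**Nothing says that an early death is scored as AKI-free.** A reader might infer that the plan deletes the worst outcomes or counts them as successes. The documents do not support that as a statement of fact. SAP 4.4.1 and 5.3 are silent, and the literal formula gives a missing value when the day-2 fluid balance is absent. Nor would an AKI-free score breach protocol 7.1.13, which requires inclusion and says nothing about scoring.

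**The 72 h and 96 h members have a purpose.** One set serving three analyses is reasonable, and SAP 5.3 already flags infants with neither early value. What remains is to report how many infants contribute to 48-hour AKI.

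**Losses are visible elsewhere.** SAP 5.2 reports withdrawals with reasons by arm, and 5.6.1 reports deaths in the safety population. This is true, but neither repairs the primary comparison.

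**The p-values are constructed.** The starting tables were chosen just under 0.05, and Fisher's exact test on 7/35 v 15/35 already gives 0.070. The population is elective, and infants with kidney dysfunction or preoperative ECMO are excluded. The figures show fragility near the threshold and are not a forecast.

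**Conclusion.** The point holds in two parts. First, SAP 3.1.1 contradicts protocol 7.1.13 for any infant who dies, or has an SAE and leaves, before the first follow-up creatinine, and the change is undeclared. An infant who leaves without an SAE is also dropped, but that departs from principle and not from 7.1.13. Second, the primary endpoint is undefined for an infant who dies or lacks the 48 h value or its fluid balance.

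The number affected is probably small and cannot be estimated from the documents. Under assumed counts near the significance threshold, the handling of one or two infants moves p across 0.05, in either direction according to the arm. This should be settled before unblinding. It is not evidence that the result will be wrong.

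**What to change.** 1. In SAP 3.1.1, define intention-to-treat as all randomised infants in their allocated arm. If a creatinine-based set is kept, call it a modified or full analysis set only, and list it in SAP section 7 as a change from protocol. Limiting the set to infants who were operated on would not solve the problem: protocol 4.3.1 places randomisation before the operation and 7.1.8 collects adverse events from randomisation, so that too is a post-randomisation exclusion.
2. In SAP 4.4.1, state one rule, fixed before unblinding and the same in both arms, for 48-hour AKI when the 48 h value or its fluid balance is missing. Do not treat a death before 48 h as AKI-free. Avoid using a lone 24 h value only when it exceeds the threshold: single-sample infants would then enter only as events and inflate the AKI rates.
3. Report the number contributing to 48-hour AKI by arm in Table 14.3.1.
4. Add a sensitivity analysis on all randomised infants, with death before 48 h counted as an event and best-case and worst-case values for other missing outcomes. Placing death here leaves the primary endpoint a kidney outcome; making it part of the primary endpoint is a separate and debatable choice.

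The cost is SAP wording and one extra table, with no new data. The downside is that the sensitivity endpoint is a composite of AKI or death.

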4 STUDY VARIABLES

4.1 Baseline Variables

4.1.1 *Screening*

- Indication (Non-restrictive VSD (corrective surgery)/Complete AVSD (bi ventricular repair)/Tetralogy of Fallot/Non-restrictive VSD with RVOT obstruction and/or PS)
- Gestational age weeks
- Gestational age days
- Gender (Male/Female)
- Age at (weeks)
- Mother's biological nationality
- Father's biological nationality

STATISTISKA KONSULTGRUPPEN		Statistical Analysis Plan	
Protocol: The prophylactic effect of Levosimendan in reducing acute kidney injury postoperatively in pediatric patients undergoing corrective heart surgery		Protocol No: MiLe-1	
		Version: 1.0	Page 8 of 17

4.1.2 *Preoperative Data*

- Pre_Weight (kg)
- Height (cm)
- Surface/area (m²)
- Diseases and/or congenital anomalies (free text coded into 0/1 variables; Mb Down, None, Other)
- Furosemide (Yes/No)
- Aldosterone (Yes/No)
- Betablocker (Yes/No)
- ACE-inhibitor (Yes/No)
- Digitalis (Yes/No)
- FS (%)
- ROSS score (Calculated value in the CRF)

4.1.3 *Preop samples taken in OR from art and cvc line*

- Hb (g/L)
- Hct
- Leucocytes (x10⁹/L)
- Trombocytes (x10⁹/L)
- CRP (mg/L)
- Na (mmol/L)
- K (mmol/L)
- Albumin (g/L)
- Creatinine(µmol/L)
- eGFR (Calculated value in CRF)
- Cystatin C (mg/L)
- Urea (mmol/L)
- NT-Pro-BNP (nanog/L)
- pH
- pCO₂ (kPa)
- pO₂ (kPa)
- ABEc (mmol/L)
- cHCO₃ (mmol/L)
- sO₂ (%)
- cLac (mmol/L)

STATISTISKA KONSULTGRUPPEN		Statistical Analysis Plan	
Protocol: The prophylactic effect of Levosimendan in reducing acute kidney injury postoperatively in pediatric patients undergoing corrective heart surgery		Protocol No: MiLe-1	Version: 1.0 Page 9 of 17

- cGlu (mmol/L)
- Ca i (mmol/L)
- Central venous sO2 (%)

4.2 Concomitant treatments and medications

4.2.1 Treatments and medication in OR

- Weaning of CPB: Only include the box “extra bolus study drug”
- Inotropic score (calculated value in CRF)
- Other medication (OR only):
 - Betablocker (YES/NO),
 - Furosemide (YES/NO),
 - Cortisone (YES/NO),
 - Cyklokpron (YES/NO),
 - Fibrinogen (YES/NO),
 - Other medication (YES/NO)
- Fluid balance (OR only):
 - Albumin (YES/NO),
 - Plasma (YES/NO),
 - RBC (YES/NO),
 - Thrombocytes(YES/NO),
 - Diuresis (in ml)

4.2.2 Treatments and medication in ICU

Concomitant medications will be presented per day (Medications in the ICU on the operative day (Status and medication_1), postop day 1 (Status and medication_2), postop day 2 (Status and medication_3), postop day 3 (Status and medication_4), postop day 4 (Status and medication_5)) and postop day 1+2 and at any time.

- Albumin infusion (Yes (>0 ml)/No(0 ml))
- Trombocyte transfusion (Yes (>0 ml)/No(0 ml))
- RBC (Yes (>0 ml)/No(0 ml), RBS in CRF miss spelling)
- Plasma (Yes (>0 ml)/No(0 ml))
- Betablocker (Yes/No)
- Cordarone (Yes/No)
- Furosemide (Yes/No)
- Furosemide (mg)
- Ethacrynic acid (Yes/No)

STATISTISKA KONSULTGRUPPEN		Statistical Analysis Plan	
Protocol: The prophylactic effect of Levosimendan in reducing acute kidney injury postoperatively in pediatric patients undergoing corrective heart surgery		Protocol No: MiLe-1	Version: 1.0 Page 10 of 17

- Ethacrynic acid (mg) (Reomax in CRF)
- hANP (Yes/No)
- Spironolactone (Yes/No)
- Spironolactone (mg)
- Methylprednisolone (Yes/No)
- Hydrocortisone (Yes/No)
- Betametason (Yes/No)
- Cortisone: Methylprednisolone, Hydrocortisone or Betametason (Yes/No)
- NO (Yes/No)
- Other medication (free text)
- Dialysis (Yes/No)
- NSAID (Yes/No, Search text Other specify field, Comments field, Extra comments and Important information:info_other_comments for NSAID, Ibuprofen, Brufen) (listing only)
- Vancomycin (Yes/No, Search text field Other specify field, Comments field, Extra comments and Important information:info_other_comments for Vancomycin, Vancocin) (listing only)
- Use of contrast (Yes/No from Important information) (listing only)
- Study drug in the PICU (Study drug in CRF):
 - Study drug according to protocol (YES/NO),
 - Milrinone started (YES/NO)

4.3 Surgery variables

Name of anesthesiologist

4.4 Efficacy Variables/Endpoints

4.4.1 Primary endpoint

AKI_(48 hours) is defined as 50% increase in corrected creatinine within 48 hours. AKI_(48 hours) is calculated using screening creatinine (uncorrected) compared to 24 and 48 hours corrected creatinine.

Corrected creatinine [(creatinine (μmol/ml)/1000 x [1 + (fluid balance (L)_(+24 hours) / (weight (kg x 0.6)))] only calculated for day 1-3. For example for day 1 the Fluid balance measured at day 2 will be used. If negative values in fluid balances, fluid balance is set to 0.

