### **2.2 Primary endpoint**

AKI is usually defined as 50% increase in creatinine within 48 hours. Accordingly, the primary outcome in this study is the postoperative creatinine levels which will be measured according to table 1.

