## 2.3 Secondary endpoints

[figure not shown]
The secondary endpoints are the hemodynamic parameters, fluid balance, the level of inflammation and other plasma kidney biomarkers (like cystatin C and NGAL), and markers of neural injury. Other parameters will also be assessed such as length of surgery, length of CPB, length of mechanical ventilation postoperatively, length of vasoactive therapy, number of vasoactive medications and total amount of infused vasoactive drugs.

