**Table 1 Study Activities**

	Pre-study	Surgery	Post-surgery				Follow-up		
			T0	T1	T2	T3	T4		
At:	Baseline		2 hours	6 hours	24 hours	48 hours	4, 5 days	30 days	
Informed consent	X								
Demography	X								
Weight, height	X								
Medical history	X								
Physical examination	X								
Inclusion/exclusion criteria	X	X							
Randomization		X							
Surgery		X							
Levosimendan/Milrinone		X	X	X	X	X			
Pulse, Blood pressure		X	X	X	X	X	X	X	
Routine laboratory screening (minimum Creatinine, S-K)		X	X	X	X	X	X	X	
Pharmacokinetics					X	X	X	X	
Study specific blood		X	X	X	X	X			
Continuous ECG monitoring		X	X	X	X	X	X		
Continuous hemodynamic and respiratory monitoring		X	X	X	X	X			
Serious Adverse event recording		X	X	X	X	X			
Urine production		X	X	X	X	X		X	
Adverse Events registr*		X	X	X	X	X	X	X	X
Registration of mortality									X
Registration of length of stay (bed-days)									X
Routine echocardiography (preoperative, after CPB termination, first postoperative day, and at discharge)									

\* Registration of adverse events will also be performed at day 30 (e.g. telephone contact with the parents if the patient is at home)

**Figure 2** *Study flow chart*

The infusion of Levosimendan/Milrinone will start perioperatively when the patient is on cardiopulmonary bypass. The infusion will thereafter continue in the intensive care unit (ICU) and will be terminated after 24 hours. Patients in both groups will be followed up according the normal clinical routines. Routine echocardiography will be performed at pre-defined time-points as a clinical routine (pre-operatively, after termination of CPB intra-operatively, at first postoperative day, and at discharge). Extra study specific blood samples will be taken from the included patients. Patients who develop AKI will be identified by increase in s-Creatinine >50% from baseline. The usual clinical and laboratory data will be routinely obtained and recorded in the hospital electronic records. Study-specific parameters will be registered in a CRF.

Follow-up of the patients will continue 4 days after termination of Levosimendan/Milrinone infusion. The follow-up parameters, included in case report form (CRF),

include among others treatment-needling hypotension, treatment-needling arrhythmias, s-Creatinine, s-Potassium and albumin.

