### **7.1.15 Evaluation and reversing of AEs**

The evaluation of the AEs will be made on the clinical and scientific basis. All caring physicians and nurses are familiar with the measures usually taken in case of adverse events. The adverse events of Levosimendan do not differ from those usually encountered in our PICU. In case of hypotension fluid therapy will be instituted initially. If the patient does not respond to the fluid therapy and hypotension is evaluated as fluid-resistant then therapy with vasoactive medications (noradrenalin, adrenalin) will be instituted. A quite common scenario is that the patient is already receiving vasoactive medication or medications as a continuous infusion or infusions, in this case a dose adjustment of the vasoactive medication or medications will be undertaken. In case of arrhythmia fluid therapy and/or anti-arrhythmic therapy, depending on the clinical situation, will be started. There are established routines in our department for dealing with post cardiac surgery arrhythmia (e.g. fluid therapy, cooling down the patient, and treatment with Amiodarone or Metoprolol). If the arrhythmia is therapy resistant pacing of the heart with routinely pre-inserted pacemaker leads will be instituted. It is noteworthy that the heart is paced routinely postoperatively in many pediatric cardiac surgery patients. In summary, the occurrence of AEs is quite usual in the setting of a post thoracic surgery intensive care unit. In these units, like our PICU, there are clinical routines for prompt recognition, evaluation, and treatment of these AEs. The probable adverse effects of Levosimendan to be encountered in this trial will not differ from the other adverse effects usually encountered in our department in connection with the use of other potent cardiovascular medications and in conjunction with cardiac surgery. A list of AEs is included in the CRF with existing appropriate fields (not related, not likely,

possible, probable, and certain) for evaluating of each AE in respect to a probable causal relationship with Levosimendan.

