### **10.2 Statistical analysis**

Analysis of data will be performed by a professional statistician. T-test for independent groups will be used for primary outcome. Descriptive statistics will be applied on the secondary outcomes including 30-days mortality, length of hospital stay and kidney function 5 days after start of infusion of Milrinone/Levosimendan. Additionally, clinical data (fluid balance, length of surgery, length of CPB, length of mechanical ventilation postoperatively, length of vasoactive therapy, number of vasoactive medications, total amount of infused vasoactive drugs, hemodynamic parameters) will be registered and analyzed. Univariate analyses will be used where needed. Multivariable regression analysis will be used to identify association between the occurrences of AKI (based on creatinine results) and the measured clinical variables.

Clinical Study Protocol  
Study Code: MiLe-1  
Drug Substance: Levosimendan  
EudraCT No: 013-003105-25  
Date

Other statistical methods might be used in an exploratory fashion but no formal inference will be made.

Safety and tolerability data will be summarized descriptively by treatment and presented in tabular and/or graphical form. All adverse event data will be listed individually and summarized using MedDRA terminology.

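### The SAP scores every AKI endpoint on fluid-corrected creatinine, the protocol on measured creatinine; the change is not declared and no planned AKI output shows whether the result depends on it

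*SAP*

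**What the plan says.** **Protocol.** Section 2.2 introduces AKI without any fluid term: "AKI is usually defined as 50% increase in creatinine within 48 hours". The text after Table 1 in section 3 gives the working rule: "Patients who develop AKI will be identified by increase in s-Creatinine >50% from baseline". Fluid balance appears only as an outcome in its own right, in section 2.3: "The secondary endpoints are the hemodynamic parameters, fluid balance".

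**SAP.** Section 4.4.1 moves the definition to a corrected value: "AKI_(48 hours) is defined as 50% increase in corrected creatinine within 48 hours". Only the postoperative side is corrected: "AKI_(48 hours) is calculated using screening creatinine (uncorrected) compared to 24 and 48 hours corrected creatinine". The multiplier is 1 + fluid balance (L)/(weight (kg) x 0.6), and a negative balance is replaced by zero. Section 4.4.3 applies the same approach to AKI at 72 and 96 hours and builds the AKI stages on corrected creatinine, with dialysis added for stage 3. The primary model in 5.5.1 is a logistic regression of corrected AKI on treatment; baseline creatinine is added if the groups differ, and fluid balance is not in the model. Table 14.3.1 covers AKI and corrected creatinine. Section 7, reserved for changes from the protocol, holds only an instruction to list them.

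**The concern.** The two documents classify children by different rules, and the SAP neither says so nor keeps the protocol's rule alongside its own. The multiplier depends on something that happens after randomisation and that treatment could affect. Protocol 7.1.4 lists hypotension as a reaction to both drugs, and 7.1.15 says: "In case of hypotension fluid therapy will be instituted initially". Two infants with the same measured creatinine can therefore be scored differently because their net balances differ.

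What is at stake is how the primary result is read. If the arms differ in AKI, or do not, a reader will ask whether this reflects measured creatinine, the correction, or both. No planned AKI analysis answers that.

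**Working it through.** **No plan figure to reproduce.** Neither document gives an expected AKI rate under either definition, a creatinine ratio or a fluid-balance distribution. The 70 patients were set on a 20% difference in creatinine, not on an AKI proportion.

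**Step 1. Definitions side by side.**

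| | Protocol 2.2 and 3 | SAP 4.4.1 and 4.4.3 |
|---|---|---|
| Postoperative value | measured | measured x (1 + FB/(0.6 x weight)) |
| Reference value | baseline, measured | screening, uncorrected |
| Negative balance | not applicable | set to 0 |
| Change declared in SAP 7 | – | no |

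FB is net fluid balance in litres. I use the formula as printed in SAP 4.4.3. The version in 4.4.1 carries a different unit and a division by 1000, and the two should be reconciled.

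**Step 2. Effect on the cut-off (arithmetic, no assumptions).** AKI is scored when measured ratio x (1 + FB/(0.6 x weight)) reaches 1.5, so the measured ratio needed is 1.5/(1 + FB/(0.6 x weight)).

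| Net balance, % of weight | Factor | Measured ratio needed | Measured rise needed |
|---|---|---|---|
| 0 or negative | 1.000 | 1.500 | 50% |
| 5 | 1 + 0.05/0.6 = 1.083 | 1.385 | 38.5% |
| 10 | 1 + 0.10/0.6 = 1.167 | 1.286 | 28.6% |
| 20 | 1 + 0.20/0.6 = 1.333 | 1.125 | 12.5% |
| 30 | 1 + 0.30/0.6 = 1.500 | 1.000 | 0% |

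The factor is never below 1, so the correction can add AKI cases but never remove them.

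**Step 3. What a difference in balance does under two opposite nulls (illustration).** Assumed inputs: creatinine ratio lognormal with median 1.2 and log-SD 0.30; net balance normal with SD 30 mL/kg, floored at 0; means of 20 and 60 mL/kg in the two arms; one time point. With no correction and no dilution, the AKI rate is P(ratio ≥ 1.5) = 1 − Φ(ln(1.5/1.2)/0.30) = 1 − Φ(0.744) = 22.8%.

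| What is equal in the two arms | AKI on measured creatinine, 20 v 60 mL/kg | AKI on corrected creatinine, 20 v 60 mL/kg |
|---|---|---|
| Measured creatinine | 22.8% v 22.8% | 27.1% v 33.6% |
| Undiluted creatinine | about 19.2% v 14.7% | about 22.8% v 22.8% |

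Under the first null the corrected definition creates a gap of 33.6 − 27.1 = 6.5 points. Under the second the measured definition creates one of 19.2 − 14.7 = 4.5 points, in the opposite direction. The documents cannot say which null is closer to the truth.

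**Step 4. Range for the first null.** With equal measured creatinine, median ratio 1.0 to 1.2, log-SD 0.3 to 0.4 and balance SD 3% of weight, a difference in mean balance of 5 points of body weight gives corrected-AKI odds ratios of 1.29 to 1.55. With 35 per arm the chance of p<0.05 favouring the drier arm is 6% to 12%, against a nominal 2.5% in that direction. A 10-point difference gives odds ratios of 1.73 to 2.30 and a chance of 16% to 34%.

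**Step 5. Search of the planned outputs.** Measured creatinine appears as a continuous laboratory value in SAP 4.4.3 and in Figure 14.4. No variable, model, table or figure is specified that scores AKI from it. The age-differentiated correction in 4.4.3 is another corrected value and is not tied to an AKI definition.

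**The case against.** The strongest reply is that the correction is there to remove a bias. Retained fluid dilutes creatinine, so equal measured values in a wetter and a drier child may mean more injury in the wetter one. The second row of the Step 3 table shows this: under that null the measured definition misleads. This stands. It is why the point is not that the corrected definition is wrong.

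Three stronger readings are tempting and are not supported:

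- *That a difference in fluid given will be read as a kidney effect.* The factor uses net balance, which falling urine output also raises, and protocol 1.3 counts reduced urine output as a sign of AKI. Part of the factor may therefore be kidney outcome. Protocol 7.1.15 also says that patients are often already on vasoactive drugs, whose dose is then adjusted. Hypotension is listed for both drugs, so nothing fixes the direction of a difference between arms.
- *That a reader could not tell kidney protection from fluid at all.* The SAP reports measured creatinine, three eGFR versions, cystatin C, NGAL, urine and fluid balance by arm. Figure 14.4 shows measured beside corrected creatinine and Figure 14.3 shows fluid overload. The gap is confined to AKI outputs.
- *That the protocol's primary outcome has disappeared.* Protocol 2.2 states that "the primary outcome in this study is the postoperative creatinine levels which will be measured according to table 1", and 10.2 adds: "T-test for independent groups will be used for primary outcome". Measured creatinine remains in the SAP as a secondary variable, with a t-test unless clearly non-normal.

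The illustration is also modest. A gap of 6.5 points is about 2 children in 35, the standard error of such a difference is about 11 points, and AKI within 48 hours uses two time points rather than one.

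**Conclusion.** The point holds in a limited form. The AKI definition changed from measured to fluid-corrected creatinine between protocol and SAP, the change is undeclared, and the protocol's definition is not analysed anywhere as AKI. The shift in the cut-off is exact: from a 50% measured rise to 38.5% at a net balance of 5% of body weight, and to 28.6% at 10%.

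The effect on the comparison between arms is not known in size or direction. The AKI rates and odds ratios above rest on assumed creatinine and fluid distributions, and they reverse when undiluted rather than measured creatinine is taken as equal. The documents support neither a claim that the primary result is biased towards one arm nor a claim that the correction should be removed. They do support a request to show how far the primary result depends on it.

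**What to change.** 1. In SAP 5.5.1 and Table 14.3.1, add the same logistic model for AKI within 48 hours scored on measured (uncorrected) creatinine at 24 and 48 hours against screening creatinine. Name it as a sensitivity analysis.
2. Show net fluid balance by arm beside the two AKI rates.
3. In SAP section 7, declare that the AKI definition differs from protocol sections 2.2 and 3, and give the dilution rationale.
4. Keep corrected AKI as primary if that is intended. Do not require both definitions to agree before a claim is made: that would give a possibly diluted measure a veto, which goes beyond a sensitivity analysis.

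All data are already collected. The cost is one derived variable, one table row and a short entry in section 7. The downside is that two AKI rates have to be explained.
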